2.4. Oxidative stress, inflammation and cardiovascular disease in chronic renal failure

Traditional risk factors, as well as additional nontraditional risk factors, can directly damage the kidney. Some studies have shown the relationship between oxidative stress and inflammatory biomarkers. Some clinical studies indicated an inverse

correlation between oxidative stress status and estimated glomerular filtration rate (eGFR) (Stevens et al., 2013).

Different mechanisms could explain the oxidative stress increase in CKD. Some conditions of CKD patients such as advanced age, diabetes, hypertension, lower levels intake of the antioxidant vitamin, and failure of ROS clearance in renal function are related to the increase of oxidative stress and progression of CKD (Meenakshi Sundaram, Nagarajan, & Manjula Devi, 2014)

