4. METHODOLOGY

4.1. Study design: A prospectively study with clinical trials, 12 months follow up.

4.2. Subject: 30 patients with hypercholesterolemia (LDL-C), stage 3-4 Chronic Kidney Disease, not receiving dialysis and 30 control participants (sex, age-matched)

4.2.1. Inclusion Criteria:

30 patients with following criteria

- CKD in the 3,4 stage (e-GFR: 15-60 ml/min/1.73 m²)
- Presence of proteinuric CKD defined as creatinine clearance >20 ml/min/1.73 m² combined with urinary protein excretion rate >0.3 g/24 h
- LDL cholesterol concentration > 100 mg/dl (2,59 mmol/l)
- Age:
 - + ≥ 50 years old but not treated with chronic dialysis or kidney transplantation
 - + In adults aged 18-49 years with CKD but not treated with chronic dialysis or kidney transplantation, we suggest statin treatment in people with one or more of the following:
 - known coronary disease (myocardial infarction or coronary revascularization)
 - diabetes mellitus
 - prior ischemic stroke
 - estimated 10-year incidence of coronary death or non-fatal myocardial infarction > 10%

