4.6. Procedure

- Potentially eligible patients attended a screening visit in an internal examination room or internal department of Hue University Hospital for medical history and other eligibility criteria checked.

- Fasting blood samples will be taken for local laboratory assays lipid profile, proteinuria, urea and creatinine, creatine kinase, SGOT, SGPT, total blood count, total haemostasis test

- If the patient satisfies the including criteria, written informed consent obtained 30 enrolled patients will be randomized into 3 groups and will receive one of 3 lipid-lowering therapies at the baseline and continue for 12 months

Group 1: (10 participants) receive 40 mg/day simvastatin (patient No 1, 4, 7...)

Group 2: (10 participants) receive ezetimibe/simvastatin 10/20 mg/day: (patient No 2, 5, 8...)

Group 3: (10 participants) receive ezetimibe/simvastatin 10/40 mg/day: 10/40: (patient No 3, 6, 9...)

- Patients will follow the treatment for 12 months and will be seen in the study clinics for routine follow-up checks and blood test at 4, 8, and 12 months.

- At each follow-up time, study treatment will be continued, unexplained muscle pain and non-study treatment recorded.

Patients are asked for an unscheduled visit if they want to have any additional review.

- If patients are unable or unwilling to attend the follow-up checks, ask them if they have any serious adverse events.

- The blood samples will be sent to Biochemical Department of Sassari University for oxidative stress indices and Tryptophan degradation indices every 4 months.

5. Biochemical analysis

- Serum Creatinine, GFR, urine protein, lipid profile, SGOT, SGPT, CK (Total Cholesterol, LDL-C, HDL-C, TG): Will be done in Hue University hospital/Hue Central Hospital.

+ Total Cholesterol, LDL-C, HDL-C, and TG were measured by enzymatic methods using commercial kits (Boehringer-Mannheim, Mannheim, Germany): Patients must fast for at least 12 hours before the test

+ Serum CK levels were measured by using a fully automated biochemical analyzer (Abbot).

+ Proteinuria

+ Serum urea, creatinine

+ Total cells blood count

+ Total hemostasis test

[Time Frame: at baseline and 4, 8, 12 months of treatment]

- Serum concentrations of Oxidative stress indices (MDA, All/UA, Taurine), Trp degradation indices (Kyn, Trp, Kyn/Trp ratio): Will be done in Sassari University hospital.

MDA, All/UA ratio, taurine, Kyn, Trp were determined by capillary electrophoresis UV detection.

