STATISTICAL ANALYSIS PLAN

LIPID-LOWERING REGIMES IMPROVE OXIDATIVE STRESS, TRYPTOPHAN DEGRADATION IN HYPERCHOLESTEROLEMIA CKD PATIENTS

Date of review: 05th May, 2018

All results will be expressed as mean values (mean SD) or median values (median and range).

The statistical differences between the mean laboratory test results patients and control group will be analyzed by ANOVA one-way statistical analysis or by Student's t-test (with Kolmogorov-Smirnov for normality).

The statistical differences in the effect of each therapy on laboratory mean values will be evaluated by one way repeated measure ANOVA with Bonferroni correction or Dunnet T3 correction, if appropriate.

To compare the differences in the median values of laboratory tests between 3 groups, ANOVA one-way will be applied. If there are statistical differences between 3 groups, we will use deeply ANOVA one-way test to analyze which group is different from another group (with Bonferroni if Levene test ≥ 0.05 or Dunnet T3 if Levene test < 0.05).

Correlation analysis between variables will be performed by Pearson's correlation or Spearman's correlation as appropriate.

Statistical analysis will be performed by using SPSS for Windows, version 20.0 (IBM Corporation; Armonk, NY, USA).

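### Arms of 10 are neither balanced nor adjusted for CKD stage, so a chance stage imbalance, which is common at this size, could be mistaken for part of a regimen effect

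*Protocol*

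**What the plan says.** **Allocation.** Protocol section 4.6 states that "30 enrolled patients will be randomized into 3 groups". The rule it then gives is a rotation by patient number, for example "10 participants) receive 40 mg/day simvastatin (patient No 1, 4, 7" and so on for group 1. No stratification or minimisation by stage or eGFR appears anywhere in the protocol.

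**Entry range.** Section 4.2.1 admits "CKD in the 3,4 stage (e-GFR: 15-60 ml/min/1.73 m²", so both stages enter. A second criterion in the same list reads "Presence of proteinuric CKD defined as creatinine clearance >20 ml/min/1.73 m²", which narrows the lower end. Creatinine is measured at the screening visit (section 4.6), so stage is known before allocation.

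**Link to the outcomes.** Section 2.4 says that some clinical studies found an inverse "correlation between oxidative stress status and estimated glomerular filtration rate (eGFR"; it gives no coefficient. Objective 2 in section 3 compares the regimens on oxidative stress indices, tryptophan degradation and renal parameters.

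**Analysis.** For the between-arm comparison the SAP says: "To compare the differences in the median values of laboratory tests between 3 groups, ANOVA one-way will be applied". Pairwise tests follow with Bonferroni or Dunnett T3. No covariate is named, and the SAP does not say that change from baseline is what is compared.

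**The concern.** Stage is a baseline characteristic that the protocol itself connects to the markers under study. For the renal parameters the connection needs no outside evidence, because eGFR defines stage: an arm with more stage-4 patients starts with lower eGFR. With 10 patients per arm, chance can leave the arms visibly different on stage. The plan neither prevents this by design nor allows for it in the analysis. If the trial turns out imbalanced, a reader cannot separate the part of an arm difference due to stage from the part due to the regimen.

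This is separate from the predictability of the rotation. Replacing the rotation with one concealed random list of 30 would leave the chance imbalance as it is.

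**Working it through.** The documents give no power, SD, stage mix or eGFR-marker correlation, so there is no stated figure to reproduce. The rotation over 30 patients does give 10/10/10.

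**Inputs.** From the documents: 30 patients, three arms of 10, stages 3 and 4, unadjusted one-way ANOVA. Assumed: 9, 12 or 15 stage-4 patients; a stage shift of 0.4, 0.8 or 1.2 within-stage SD; two-sided alpha 0.05; allocation truly random.

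**Step 1: how often the arms differ on stage.** With K stage-4 patients, the chance of counts a, b, c in the three arms is C(10,a)·C(10,b)·C(10,c) / C(30,K). For K = 12, C(30,12) = 86,493,225:

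- Range 0 (4/4/4): 210³ = 9,261,000, or 10.7%.
- Range 1 is impossible, because 12 is divisible by 3.
- Range 2 (5/4/3, six orders): 6 × 252 × 210 × 120 = 38,102,400, or 44.1%.
- Range 3 (5/5/2 and 6/3/3, three orders each): 3 × 252² × 45 + 3 × 210 × 120² = 17,645,040, or 20.4%.
- So range 3 or more is 45.2%, and range 4 or more is 24.8%.

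| Stage-4 patients of 30 | 2 or more | 3 or more | 4 or more |
|---|---|---|---|
| 9 | 88% | 40.4% | 20.4% |
| 12 | 89% | 45.2% | 24.8% |
| 15 | 90% | 46.7% | 26.2% |

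If the clearance criterion leaves only 5 or 6 stage-4 patients, the chances are 32% and 30% for 3 or more, and 9% and 12% for 4 or more. All these figures are for the largest gap among three pairs. Summing the same formula for one pair named in advance, with K from 9 to 15, gives 23-27% for 3 or more and 9-12% for 4 or more.

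**Step 2: size of the bias.** Bias in a pair difference = (difference in stage-4 count / 10) × stage shift. With 12 of 30 in stage 4, stage adds about 0.4 × 0.6 × shift² to the marker variance. The unadjusted pair standard error is therefore √[0.2 × (1 + 0.24 × shift²)], in within-stage SD.

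| Shift | Bias at 3 | Bias at 4 | Pair SE | Share of variance due to stage |
|---|---|---|---|---|
| 0.4 | 0.12 | 0.16 | 0.46 | 0.0384/1.0384 = 4% |
| 0.8 | 0.24 | 0.32 | 0.48 | 0.1536/1.1536 = 13% |
| 1.2 | 0.36 | 0.48 | 0.52 | 0.3456/1.3456 = 26% |

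The bias stays below one standard error throughout. The last column is roughly the variance that adjustment could remove, before its cost of one degree of freedom.

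**Step 3: false-positive rate of the planned ANOVA.** Null trials were simulated with 12 stage-4 patients randomly permuted over the three arms and no treatment effect. Repeat runs differ by up to about 0.3 percentage points.

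| Shift | All trials | Given 3 or more | Given 4 or more |
|---|---|---|---|
| 0.4 | about 5% | 5.3% | 5.8% |
| 0.8 | about 5% | 6.5% | 7.3% |
| 1.2 | about 5% | 7.9% | 10.1% |

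With stage in the model, the conditional rates return to about 5%.

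**Step 4: effect of stratifying.** Permuted blocks of three within stage hold the stage-4 difference between any two arms to at most 1, if all 30 are enrolled.

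**The case against.** Simple randomisation is valid. Chance imbalance is already part of the ANOVA's error variance, so over all allocations the test holds its 5% level. A reader might infer from the imbalance that the planned test is invalid, or that a stage difference would necessarily pass for a regimen effect. The documents and the calculation do not support either reading: lower rejection rates in balanced trials offset the excess in imbalanced ones. What remains is bias given the allocation actually obtained, and that matters to whoever interprets the one trial that is run.

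It is also tempting to put a 0.24 or 0.32 SD shift into a noncentral t test and read off 8.1% and 10.6%. That treats the SD as free of stage variation. Allowing for it, pairwise rejection is about 6.1% and 8.3% at differences of exactly 3 and 4. The SAP in any case tests pairs only after a significant ANOVA, and with correction.

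The prognostic premise is modest. Section 2.4 cites some studies without a coefficient and also lists age, diabetes and hypertension without ranking them, so calling stage the strongest factor would go too far. The clearance criterion makes the real eGFR range narrower than 15-60.

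The SAP's within-arm analysis ("The statistical differences in the effect of each therapy on laboratory mean values will be evaluated by one way repeated measure ANOVA") is unaffected by between-arm imbalance. A comparison of changes from baseline would also remove a stable level difference due to stage. But the within-arm tests do not answer the comparative objective, and the SAP does not commit to comparing changes.

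Finally, adjustment alone corrects most of the problem, so stratification is not the only remedy. That stands.

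**Conclusion.** The point holds as an improvement to a small trial. The plan neither balances nor adjusts for CKD stage. With 9 to 15 stage-4 patients, a difference of 2 or more between some two arms is likely (88-90%). A difference of 3 or more occurs in 40-47% of random allocations, and of 4 or more in 20-26%. Given such an imbalance, the planned ANOVA's false-positive rate is about 5.3-7.9% (3 or more) or 5.8-10.1% (4 or more) for shifts of 0.4 to 1.2 SD. The unconditional rate stays at 5%. An imbalance could therefore be mistaken for part of a regimen effect, but need not be.

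The stage mix and the shifts are assumptions, because the documents give neither. The figures also take allocation as random. The rotation in section 4.6 is predictable, and any imbalance from selective enrolment would come on top and is not covered here.

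**What to change.** - **Protocol 4.6:** replace the rotation by patient number with concealed random allocation, 1:1:1 in permuted blocks, within two strata: CKD stage 3 and stage 4 by screening e-GFR. With 30 patients, stage should be the only stratifier.
- **SAP:** include stage, or baseline eGFR, as a term in the between-arm model. If stratification proves impractical, this step alone recovers most of the benefit.
- **Protocol 4.2.1:** reconcile the e-GFR range with the creatinine clearance criterion, so that the expected stage mix is clear.

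**Cost:** two lists instead of one, using a value already obtained at screening; one degree of freedom in the model; and arm sizes that may be 9 to 11 instead of exactly 10.

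### Section 4.6 calls the allocation randomized but fixes each arm by rotating patient number, with no random numbering or concealment described, so the comparison of the three regimens is open to selection bias.

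*Protocol*

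**What the plan says.** Protocol section 4.6 places screening and eligibility checks first. It then says, after written consent, that "30 enrolled patients will be randomized into 3 groups and will receive one of 3 lipid-lowering therapies at the baseline". The lines that follow give the rule:

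- "Group 1: (10 participants) receive 40 mg/day simvastatin (patient No 1, 4, 7", and so on
- "Group 2: (10 participants) receive ezetimibe/simvastatin 10/20 mg/day: (patient No 2, 5, 8", and so on
- "Group 3: (10 participants) receive ezetimibe/simvastatin 10/40 mg/day: 10/40: (patient No 3, 6, 9", and so on

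Neither document says how, when or by whom patient numbers are issued. Neither mentions a random list, allocation concealment or blinding, and the SAP does not mention allocation at all.

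The comparison that depends on allocation is Objective 2 in Protocol section 3. The SAP's analysis for it is: "To compare the differences in the median values of laboratory tests between 3 groups, ANOVA one-way will be applied". If that test is significant, pairwise comparisons follow, with Bonferroni or Dunnett T3 chosen by Levene's test. No baseline adjustment is named, and the SAP does not say whether follow-up values or changes are analysed.

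**The concern.** The word used is randomization, but the rule printed beneath it is systematic allocation. Once a patient's number is known, so is the arm. If numbers run in order of enrolment, which is the natural reading, staff know the next patient's regimen before approaching anyone. The screening visit supplies lipids, proteinuria, creatinine and creatine kinase before allocation, so prognostic information is at hand when someone decides whom to enrol next, or when.

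A baseline difference produced in this way would carry into the arm difference, because nothing in the SAP removes it. The trial could also be reported as randomized when its only documented allocation method is not. The comparison of patients with matched controls and the within-therapy analyses do not rest on this allocation and are unaffected.

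**Working it through.** **Reproducing the plan's own figure.** Assigning numbers 1 to 30 by remainder on division by 3 gives 10 + 10 + 10 = 30. The group sizes agree with the rule; the question is only whether the rule is random.

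**How much can be foreseen.** Rotation in enrolment order allows one sequence, so 30/30 = 100% of assignments are known. A random list constrained to 10/10/10 has 30!/(10!)³ ≈ 5.55 × 10¹² possible sequences. For someone who sees all past assignments and always guesses the arm with most places left, exact recursion gives:

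- expected correct guesses 13.70, and 13.70/30 = 45.7%
- expected assignments certain in advance (only one arm still open) 1.43 of 30

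By simulation, permuted blocks of 3 are about 61% guessable and blocks of 6 about 56%.

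**What an imbalance could do (illustration only).** The documents give no figure for the shift or the correlation, so both are assumed. Suppose there is no true treatment effect, 10 complete patients per arm, equal SDs, one arm's baseline mean shifted by d SD, baseline/follow-up correlation r, and a nominal 5% test.

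- Follow-up values analysed: shift = r·d, with SD 1.
- Changes analysed: shift = (r − 1)·d, with SD √(2(1 − r)).
- With δ = shift/SD, the noncentrality is λ = 10·δ²·(2/3), and the ANOVA has 2 and 27 df (critical F 3.35).

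Example, d = 0.5 and r = 0.8, follow-up values: δ = 0.40, λ = 10 × 0.16 × 2/3 = 1.07, rejection rate 12.9%. Example, d = 0.5 and r = 0.3, changes: δ = −0.35/√1.4 = −0.296, λ = 0.583, rejection rate 9.1%.

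| d = 0.5 | Follow-up: shift (SD) | Error | Changes: shift (SD) | Error |
|---|---|---|---|---|
| r = 0.3 | +0.15 | 6.0% | −0.35 | 9.1% |
| r = 0.5 | +0.25 | 7.9% | −0.25 | 7.9% |
| r = 0.8 | +0.40 | 12.9% | −0.10 | 6.1% |

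If d runs from 0.25 to 1.0 over the same correlations, the error runs from 5.2% to 39.9% for follow-up values and from 5.3% to 23.4% for changes.

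In simulations of 6,000 trials per case at d = 0.5, ANCOVA on the shifted baseline held the error at 4.9% to 5.3%. That is the favourable case, since only a measured baseline was shifted.

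**The case against.** The strongest reply is that enrolment-order numbering is an inference. The text puts consent before allocation and speaks of enrolled patients, so numbers might be issued after enrolment, or at random. This has some force: in the first case the opportunity moves from choosing whom to enrol to deciding who gets which number, and random numbers drawn after consent would make the rule harmless. But neither arrangement is written down. Random numbering alone would not be enough either, because a number visible before consent still reveals the arm. The protocol has to change on any reading.

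Eligibility rests partly on numeric laboratory thresholds, and the outcomes are mainly assays, some run in another country. That narrows discretion and limits measurement bias. It does not remove the choice of whom or when to enrol.

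The size of the illustrated bias depends on a shift that has no source in the documents. This stands, and the wide range above shows it. The conclusion rests on the allocation rule, not on those rates.

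A single list is one choice among several. Permuted blocks would hold the arms closer if recruitment stops early, but they are easier to guess.

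**Conclusion.** The concern holds. As written, section 4.6 specifies a non-random rule under the name of randomization, and nothing in either document makes the numbers random or conceals them. If numbers follow enrolment order, 30 of 30 assignments are foreseeable, against about 1.4 certain and at best 45.7% guessable under a single random list. The consequence is confined to the comparison of the three regimens. Whether bias has occurred, and how large it would be, cannot be determined from the documents. This should be corrected before the between-arm comparison is described as randomized.

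**What to change.** **Section 4.6.** Replace the patient-number rule with one computer-generated permuted list of 30, constrained to 10/10/10 and held by someone not involved in recruitment. Put the assignments in sequentially numbered, sealed, opaque envelopes, opened only after eligibility and consent are confirmed.

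**If some patients have already been allocated by rotation.** This is possible, since the protocol is dated May 2018 and the stated start is November 2017. Use a permuted list for the remaining places so that the totals still end at 10/10/10. For example, if 12 were already allocated, a list of 18 places with 6 per arm would be at best 48.6% guessable. Report the earlier patients as systematically allocated and do not call the trial fully randomized. In the SAP, analyse the between-arm comparison by ANCOVA on each outcome's baseline value, naming the visit or visits (months 4, 8, 12) to which it applies. Replace the Levene-based choice, including "Dunnet T3 if Levene test < 0.05", with Bonferroni-adjusted comparisons of the adjusted means. Adjustment covers measured baseline values only and does not restore randomization. If all 30 are already allocated, only the reporting and the adjustment remain possible.

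**Cost.** One paragraph, one list and up to 30 envelopes, with no extra patients, visits or assays. A list holder outside recruitment is an assumption, as the documents describe no staffing.

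- If recruitment stops early, a single list can leave uneven arms: the largest exceeds the smallest by 3 or more in 50.0% of lists at 20 patients, 30.1% at 24 and 8.9% at 27. Rotation never exceeds 1.
- If ANCOVA is needed, it costs one error df: 26 against 27 with 30 complete patients, 20 against 21 with 24 (section 4.6 anticipates missed visits). The Bonferroni critical t for three comparisons moves from 2.552 to 2.559, or from 2.601 to 2.613.
- Dropping Dunnett T3 gives up its allowance for unequal variances.
- Reporting is less favourable if rotation has been used.

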(1) Do different lipid-lowering drugs (simvastatin monotherapy and ezetimibe/simvastatin combination therapy) have a different impact on the lipid profile, oxidative stress indices, Tryptophan degradation?

(2) Does statin monotherapy or co-administration of ezetimibe ameliorate the renal dysfunction in CKD patients?

(3) How do lipid-lowering therapy effect on lipidemia disorders in patients with CKD by mechanism involved in oxidative stress and tryptophan?

(4) Are the unexpected effects on muscle problem and hepatic enzyme profile of long-term statin monotherapy and statin/ezetimibe combination therapy a big concern?

II. REVIEW OF RESEARCH LITERATURE

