2.12. Simvastatin

- Treat with statins for 1-2 weeks, up to 4-6 weeks, and maintain during long-term treatment.
- Simvastatin largely excreted in the feces. Approximately 10-15% of the drug excreted by the kidney
- Dosage is 5-80 mg/day, in the evening.
- No dosage adjustment is needed in the elderly
- **Contraindications of Simvastatin:**
 - + Active liver disease or unexplained persistent elevations of serum transaminases

- + Pregnancy and lactation
- + Concomitant administration of potent CYP3A4 inhibitors (e.g. itraconazole, ketoconazole, posaconazole, HIV protease inhibitors (e.g. nelfinavir), erythromycin, clarithromycin, telithromycin, and nefazodone)
- + Concomitant administration of gemfibrozil, ciclosporin, or danazol.
- **Unexpected effects of Simvastatin and how to manage unexpected effects**
 - + **Myopathy:** The risk of myopathy is related to dose. In a clinical trial of 41,413 patients treated with simvastatin, 24,747 patients (about 60%) with an average follow-up of at least 4 years, the incidence of myopathy was approximately 0.03%, 0.08% and 0, 61% at doses of 20, 40 and 80 mg/day, respectively.
 - If the patients have muscle aches, weakness or cramps, do CK test. If CK increases (> 5 times) discontinue treatment, re-assess levels within 5 to 7 days.
 - If the muscular symptoms are severe and cause daily discomfort, even if the CK levels are < 5 times normal, consider stopping treatment.
 - + **Elevated liver enzymes:** Continuous elevations (up to > 3 times) liver enzymes have occurred in some patients receiving simvastatin.
 - When simvastatin is discontinued, the level of transaminase usually decreases gradually down to the pre-treatment level.

+ **Diabetes Mellitus**

Some evidence suggests that statins as a class raise blood glucose and in some patients, at high risk of future diabetes, may produce a level of hyperglycemia where formal diabetes care is appropriate. This risk, however, is outweighed by the reduction in vascular risk with statins and therefore should not be a reason for stopping statin treatment.

+ Other side effects: Dizziness, fainting, fast or irregular heartbeat,...

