2.14. New York Heart Association class III (McMurray et al., 2012)

Classification of heart failure symptoms

Class I	People whose physical activity is not limited. Ordinary physical activity does not cause undue fatigue, heart palpitations, trouble breathing, or chest pain.
Class II	People who have some limitation on physical activity. They are comfortable at rest, but ordinary physical activity causes fatigue, heart palpitations, trouble breathing, or chest pain.
Class III	People who have a marked limitation on physical activity. They are comfortable at rest, but less-than-ordinary physical activity causes fatigue, heart palpitations, trouble breathing, or chest pain.
Class IV	People who are unable to carry on any physical activity without discomfort. Symptoms may be present even at rest. If any physical activity is done, discomfort increases.

2.15. 2017 Taiwan lipid guidelines for high-risk patients

LDL-C increased CV risk in patients with CKD. In adults with glomerular filtration rate (GFR) < 60 mL/min/1.73m² without chronic dialysis (CKD stage 3-5), statin therapy should be initiated if LDL-C ≥ 100 mg/dL. Ezetimibe can be added to a statin to consolidate the CV protection in CKD patients (Li et al., 2017)

3. Objective of the research

The target of this study is to focus on mechanisms underlying dyslipidemia in CKD and clinical trial evidence for lipid lowering therapy in patients with CKD via parameters of lipid, oxidative stress, tryptophan degradation as well as renal function, in comparison to statin/ezetimibe therapies in CKD patients with dyslipidemia.

- 1) To verify the effect of lipid lowering therapies on lipid profile and inflammatory status in Vietnamese CKD population. [Time Frame: at the baseline and at 4th month, and one-year following].
- 2) To compare the effect of lipid-lowering regimes (simvastatin mono-therapy and EZE/simvastatin 10/20, EZE /simvastatin 10/40 combination therapy) on lipid profile, oxidative stress indices, Tryptophan degradation, renal parameter, and side effect in Vietnamese CKD patient. [Time Frame: after the 4th month, 8th month and one-year following].

We hope with scientific evidence, doctors will well understand the mechanism, effect, and safety of potential and existing therapies. Therefore, the prescription rate of lipid-lowering drugs and control rate of hyperlipidemia could be increased in CKD

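### Side effects are compared between regimens, but stops and between-visit CK or transaminase results are not listed as data, and the SAP has no by-arm count of stops or muscle pain

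*Protocol*

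**What the plan says.** **The question.** Objective 2 (Protocol section 3) lists among the outcomes compared between regimens "renal parameter, and side effect in Vietnamese CKD patient". Research question 4 (section I) asks: "Are the unexpected effects on muscle problem and hepatic enzyme profile of long-term statin monotherapy and statin/ezetimibe combination therapy a big concern".

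**The data.** Section 4.6 gives the clinical content of a follow-up visit in one sentence: "At each follow-up time, study treatment will be continued, unexplained muscle pain and non-study treatment recorded". For patients who do not come, it says: "If patients are unable or unwilling to attend the follow-up checks, ask them if they have any serious adverse events". Extra visits are possible: "Patients are asked for an unscheduled visit if they want to have any additional review". No test or data item is attached to them. Section 5 lists CK, SGOT and SGPT with the schedule "Time Frame: at baseline and 4, 8, 12 months of treatment".

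**Management of side effects.** The only text is section 2.12, under the heading "II. REVIEW OF RESEARCH LITERATURE". It advises a CK test for muscle symptoms, stopping if CK rises more than 5 times with a recheck in 5 to 7 days, and a further ground for stopping: "If the muscular symptoms are severe and cause daily discomfort, even if the CK levels are < 5 times normal, consider stopping treatment". Section 4.6 does not refer to it.

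**The analysis.** The SAP expresses results as mean with SD or median with range. It compares the three arms on laboratory tests by one-way ANOVA. It mentions no counts, proportions, adverse events or discontinuations.

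**The concern.** A comparison of side effects needs to know who had symptoms, who stopped and why. The plan collects part of this (muscle pain at attended visits, scheduled enzymes) and analyses less of it (laboratory averages). Two arms could show similar scheduled CK values while patients in one of them had muscle pain or stopped because of it. The side-effect part of objective 2 would then be answered from laboratory averages alone. Stop dates, reasons and between-visit results may also be harder to reconstruct if nobody is told to write them down at the time.

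**Working it through.** The plan states no figure on this point, so there is none to reproduce. The check sets the texts side by side and then asks what the planned test can register.

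**1. Is a stop captured?** The sentence in 4.6 can be read two ways: study treatment continues while pain and other treatment are recorded, or all three are recorded. On either reading, no stop, date or reason is named. The question prescribed for non-attenders concerns serious adverse events, and stopping for troublesome but non-serious muscle pain need not be one.

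**2. Is the relevant enzyme value captured?**
- CK prompted by pain at a month 4, 8 or 12 visit: yes, it falls on the schedule in section 5.
- CK at an unscheduled visit, or a recheck 5 to 7 days after a high value: not listed.
- Stop for severe symptoms with CK below 5 times normal (foreseen in 2.12): no comparison of CK can show it.

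**3. What does the between-arm ANOVA see?** Inputs: 3 arms of 10 (section 4.6), and one patient whose CK exceeds everyone else's by a large amount X. Taking the other 29 values as equal:
- The affected arm's mean is raised by X/10 and the grand mean by X/30.
- Between-arm sum of squares = 10(X/10 − X/30)² + 20(X/30)² = X²/15.
- Within-arm sum of squares = X² − 10(X/10)² = 0.9X².
- F = (X²/15 ÷ 2) / (0.9X² ÷ 27) = 0.0333/0.0333 = 1 on 2 and 27 degrees of freedom.
- p = (1 + 2F/27)^(−13.5) = (1.0741)^(−13.5) = 0.38.

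X cancels, so a larger CK does not lower p. A simulation agrees. The other values were drawn as normal with assumed means of 0.3, 0.5 or 0.7 and SDs of 0.1 to 0.2 times the upper limit, and one value was set to 6, 10 or 20. Median p was 0.38 to 0.39, the smallest was 0.107, and none of 36,000 runs fell below 0.05. This restates the algebra rather than adding to it.

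With two such patients in the same arm, the sums of squares are 0.267X² and 1.6X², so F = 0.1333/0.0593 = 2.25 and p is about 0.12.

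**4. What do the summaries show?** With one CK of 6 times the upper limit and nine at b, the arm mean is (9b + 6)/10 = 0.87, 1.05 or 1.23 for b = 0.3, 0.5 or 0.7. The arm SD is (6 − b)/√10 = 1.80, 1.74 or 1.68, against the 0.1 to 0.2 assumed for the other patients. A reader of mean and SD, or of median and range, would notice.

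**5. How many events?** Section 2.12 gives myopathy rates of 0.03% at 20 mg and 0.08% at 40 mg, from a trial with longer follow-up. Expected cases are at most 10 × 0.0008 + 10 × 0.0003 + 10 × 0.0008 = 0.019. The documents give no rate for milder stops. If it were 1%, 5% or 10% (assumed only to show the range), the chance of at least one stop in 30, 1 − (1 − r)^30, is 26%, 79% or 96%.

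**6. What can counts show?** The exact 95% interval is 0 to 30.8% for 0/10 and 0.25 to 44.5% for 1/10. Fisher's two-sided test for 10 against 10 gives p = 0.087 at 4 against 0 and p = 0.033 at 5 against 0.

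**The case against.** The best defence is that most of the safety data already exist. Muscle pain, CK, SGOT and SGPT are gathered at the visits, and nothing forbids the investigator from tabulating pain by arm or asking a non-attender more than the protocol prescribes. Section 2.12 is worded as management instructions and stands in the protocol. Myopathy is very unlikely here, side effects come last in objective 2, and no method would establish a difference from one case in 10.

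Much of this stands. The protocol does contain guidance on stopping, even though 4.6 does not adopt it. The muscle-pain gap is one of analysis, not of collection at attended visits. The ANOVA's failure to flag a single case is no special defect, since Fisher's test would not flag it either. The difference is that a count displays the case in the arm where it occurred, while a p-value of 0.38 reads as no difference.

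The defence does not supply a stop date, a reason or a between-visit result. If 2.12 does apply, its recheck and its symptom-based stops are the items that 4.6 and section 5 leave out.

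A reader might go further and infer that a high CK would be invisible unless the SAP's median-and-range format were chosen. That is wrong: step 4 shows that the SD would reveal it too. Nor do the documents show that stops are likely, or that missing details could never be recovered from hospital records.

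**Conclusion.** The point holds as a gap between a stated comparison and the data and analysis planned for it. Followed as written, the protocol can miss stops for non-serious symptoms and does not list between-visit CK or transaminase results. The SAP would judge muscle and liver effects by a test of means that does not register one patient crossing a threshold (p about 0.38, whatever the value).

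The p-value rests on 10 patients per arm and one value far above the rest, and multiples of CK are taken relative to the upper limit of normal. The number of stops to expect is unknown: the 26% to 96% range reflects assumed rates only. The trial is not invalidated, and the lipid, oxidative-stress and tryptophan comparisons are not the subject here. The change should be made because it is cheap and gives a direct descriptive answer to the trial's own question. Whether patients who stop stay in the sampling and analysis, and whether peak values per patient are reported, are separate or optional matters.

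**What to change.** - **Section 4.6:** at every contact, including contacts with non-attenders, record whether study treatment is being taken, the date and reason of any stop, and muscle pain.
- **Section 5:** add the dated result of any unscheduled CK, SGOT or SGPT to the dataset.
- **SAP:** report by assigned arm, descriptively and with exact 95% intervals, the number of patients who stopped (with reasons), with unexplained muscle pain, with CK above 5 times, and with transaminases above 3 times. State the reference limit for each multiple. Show scheduled and unscheduled values separately.

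The cost is a few form fields and one table; no visit or test is added. Unscheduled tests are driven by symptoms, so they must not be pooled with scheduled ones. With 10 per arm, the counts describe and do not establish a difference between regimens.
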